#### 6.8.2.3. TO ANALYZE DIFFERENTIALLY EXPRESSED CYTOKINES AS BIOMARKERS OF DISEASE PROGRESSION IN EARLY, MID, AND LONG PERIODS OF IMMUNIZATION

Cytokine levels will be studied and compared between different clinical spectrum or sexes to determine their role as a biomarker of disease type. Appropriate statistical tests (i.e. t-test or Mann-Whitney to compare between sexes and ANOVA or Kruskal-Wallis to compare between clinical spectrums) will be used after checking for normality (Shapiro-test). Significance level will be set to 0.05. All the analyses will be performed using R version 3.6.3 or higher.

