## 5. HYPOTHESES AND OBJECTIVES

### 5.1 HYPOTHESES

The specific hypotheses are:

Infection with SARS-CoV-2 will produce different levels of immune response with respect to:

1. The kinetics and immune response is different depending on the clinical spectrum of COVID-19 disease.
2. The immune response is conditioned by age, sex and other clinical variables
3. Cytokines are good biomarkers to identify COVID-19 disease progression.

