### 5.2.2 SECONDARY AIM

1. To determine the kinetics of SARS-CoV-2 antibodies and cellular immune response in early, mid, and long periods of immunization.
2. To assess the relation between clinical variables and initial RT-PCR results with the interindividual differences in the immune response in early, mid, and long periods of immunization.
3. To analyze differentially expressed cytokines as biomarkers of disease progression in early, mid, and long periods of immunization.

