[Time Frame: Baseline, 7 days, 15 days, 3, 6, 9 and 12 months after the beginning of the study]

10. Cytokines as biomarkers of disease progression in early, mid, and long periods of immunization.

Cryopreserved plasma samples will be used in a 45-plex assay of soluble mediators. The plates will be read with a Luminex instrument (Luminex 200, Austin Luminex, USA).Appropriate statistical tests (i.e. t-test or Mann-Whitney to compare between sexes and ANOVA or Kruskal-Wallis to compare between clinical spectrums) will be used after checking for normality (Shapiro-test)

[Time Frame: Baseline, 7 days, 15 days, 3, 6, 9 and 12 months after the beginning of the study]

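### A between-sex cytokine test is offered as evidence on disease biomarkers, and the clinical-spectrum comparison that does bear on them is not adjusted for sex

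*Combined protocol and SAP*

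**What the plan says.** Section 6.8.2.3 gives one purpose for two comparisons: "Cytokine levels will be studied and compared between different clinical spectrum or sexes to determine their role as a biomarker of disease type". It then names the tests, "t-test or Mann-Whitney to compare between sexes and ANOVA or Kruskal-Wallis to compare between clinical spectrums", with a Shapiro test to choose between the parametric and rank versions, and adds "Significance level will be set to 0.05". Section 6.6.2, secondary outcome 10, titled "Cytokines as biomarkers of disease progression in early, mid, and long periods of immunization", names the same pair of tests. The assay is described there: "Cryopreserved plasma samples will be used in a 45-plex assay of soluble mediators".

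The aim served is secondary aim 3 (section 5.2.2): "To analyze differentially expressed cytokines as biomarkers of disease progression in early, mid, and long periods of immunization". Section 5.1 states two separate hypotheses. Hypothesis 3 is "Cytokines are good biomarkers to identify COVID-19 disease progression". Hypothesis 2 is "The immune response is conditioned by age, sex and other clinical variables".

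For cytokines, the documents give no sex-adjusted or sex-stratified spectrum comparison and no sex-by-spectrum interaction. They do not say that only the spectrum comparison supports a biomarker conclusion. Secondary outcomes 8 and 9 specify analysis in the full sample and by sex; outcome 10 does not.

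**The concern.** The conclusion sought is about disease, but one of the two tests offered for it takes only cytokine level and sex as inputs. Its null hypothesis is that men and women have the same level. A constitutional sex difference rejects that null whether or not the cytokine has anything to do with COVID-19. A cytokine that rises with severity equally in both sexes need not reject it. The plan itself expects sex to affect the immune response (hypothesis 2), so it anticipates the kind of difference that section 6.8.2.3 would then read as bearing on disease type.

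Sex also matters for the other comparison. If men and women differ in severity mix, the clinical-spectrum groups differ in sex composition. A cytokine that differs only by sex will then differ between spectrum groups. Without adjustment, the relevant test can itself confuse a sex marker with a disease marker. With 45 analytes, the findings reported under hypothesis 3 could mix the two.

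**Working it through.** **1. The logical step, which needs no numbers.** Hypothesis 3 concerns the relation of cytokine to disease. The spectrum ANOVA or Kruskal-Wallis tests that relation. The t-test or Mann-Whitney by sex tests the relation of cytokine to sex, which belongs to hypothesis 2.

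**2. The plan's only power figure, for scale.** Section 6.4 is for the two-cohort comparison, not for cytokines, and the point does not depend on it. With η² = 0.01, f² = 0.01/0.99 = 0.0101 and f = 0.1005, so d = 2f = 0.201 for two equal groups. The noncentral F with 2 groups and α = 0.05 gives 522 per group (power 0.9005), which reproduces the stated figure. I use d = 0.201 as one illustrative effect size.

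**3. What the sex test responds to.** Assumptions: 675 infected (the planned cohort; the number assayed for cytokines may be smaller), 50% to 80% women, two-sided α = 0.05, and a cytokine unrelated to disease. SE = √(1/n_women + 1/n_men) in SD units; power ≈ Φ(d/SE − 1.96).

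| Women | n women / n men | SE | d = 0.201 | d = 0.3 | d = 0.5 |
|---|---|---|---|---|---|
| 50% | 337.5 / 337.5 | 0.0770 | 0.74 | 0.97 | >0.99 |
| 80% | 540 / 135 | 0.0962 | 0.55 | 0.88 | >0.99 |

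Example, 80% women: 0.201/0.0962 − 1.96 = 0.13, and Φ(0.13) = 0.55. These values are the test's power to find an assumed real sex difference.

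**4. The reverse case.** Simulation of 4,000 runs: 675 participants, 70% women, severity mix 25/65/10% (asymptomatic, mild-moderate, severe-critical), severity unrelated to sex, severity shifts of 0, 0.25 and 0.5 SD, and no sex effect. The sex test rejects in 4.7% of runs, which is the chance rate. The spectrum ANOVA rejects in 92%.

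**5. The spectrum comparison when sex and severity are associated.** Same size and sex split, 4,000 runs per setting, and no severity effect on the cytokine. Women keep the mix 25/65/10%. Men have 15/65/20% (10-point shift) or 5/65/30% (20-point shift).

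The mechanism can be followed by hand for a 0.5-SD sex difference:
- 10-point shift: the share of men is 0.045/0.220 = 0.205 in the asymptomatic group and 0.060/0.130 = 0.462 in the severe-critical group. The induced mean difference is 0.5 × (0.462 − 0.205) = 0.13 SD.
- 20-point shift: the shares are 0.015/0.190 = 0.079 and 0.090/0.160 = 0.563. The induced difference is 0.5 × (0.563 − 0.079) = 0.24 SD.

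Simulated rejection rates at 0.05:

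| Shift in severity mix | Sex difference (SD) | Sex t-test | Spectrum ANOVA, unadjusted | Spectrum test, sex-adjusted |
|---|---|---|---|---|
| none | 0.201 | 66% | 5.6% | 5.5% |
| none | 0.5 | about 100% | 4.9% | 4.9% |
| 10 points | 0.201 | 67% | 6.2% | 5.2% |
| 10 points | 0.5 | 100% | 12.7% | 5.6% |
| 20 points | 0.201 | 67% | 9.2% | 5.1% |
| 20 points | 0.5 | 100% | 34.8% | 4.6% |

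A noncentral F calculation from the induced means gives 12% and 35% for the two 0.5-SD rows with a shift, in agreement with the simulation.

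**The case against.** The strongest reply is that this is loose drafting. The protocol pairs clinical spectrum with sex throughout: in the LOESS curves, the nonlinear mixed models and the antibody comparisons. Section 6.8.2.3 may simply compress that template into one sentence. A sex comparison of cytokines has a legitimate purpose under hypothesis 2, since section 6.6.2 counts cytokines among the immune-response outcomes. Each test is tied to its own contrast and nothing pools their results. Section 4 describes cytokine testing as more exploratory, and this is one secondary outcome of an observational cohort.

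Much of this stands, and it rules out three stronger readings that a reader might infer:
- *That the plan credits any cytokine differing by sex as a disease biomarker.* There is no criterion for declaring a biomarker. The text gives a purpose, two tests and a significance level.
- *That the planned output cannot answer the biomarker question.* The spectrum comparison is planned separately and is the right one in kind.
- *That the 55% to 97% in step 3 at d = 0.201 and 0.3 are false-positive rates.* They are the power to detect an assumed real sex difference. They would become errors only if that result were read as evidence on disease.

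Nor is it exact to say that the sex test carries no disease information. If sex and severity are associated it carries some, but only indirectly and confounded.

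The reply does not remove the stated purpose, which attaches the sex test to disease type in 6.8.2.3, with the same tests repeated under outcome 10. It also does not supply the missing sex adjustment.

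**Conclusion.** The point holds. Section 6.8.2.3 and outcome 10 offer a between-sex test as evidence on disease biomarkers when it addresses hypothesis 2, and this conclusion rests on no numerical assumption. The spectrum comparison is the relevant one, but it is open to confounding by sex. Its size depends on quantities that the documents do not give. With 675 infected, 70% women and a 25/65/10% severity mix in women, a cytokine with a 0.5-SD sex difference and no disease effect is flagged in 13% of runs for a 10-point shift in severity mix and 35% for a 20-point shift, against about 5% after adjustment. With a 0.201-SD sex difference the inflation is small (6% to 9%), and with no association between sex and severity there is none. The defect is confined to a secondary aim and is worth correcting because the correction is cheap.

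**What to change.** In section 6.8.2.3 and secondary outcome 10:
1. Delete the reference to sexes from the sentence on biomarker purpose.
2. State that biomarker conclusions rest only on the comparison of cytokine level across clinical spectrum, adjusted for or stratified by sex, for example a linear model of log cytokine on spectrum plus sex.
3. Report crude sex differences descriptively under hypothesis 2, as not bearing on biomarker status.
4. If sex-specific biomarkers are of interest, add a sex-by-spectrum interaction and say so.

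The cost is a few lines of text and one linear model per cytokine, 45 at each time point analysed. Sex is already recorded, so no new data are needed.

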## 6. METHODS

### 6.1. DESIGN:

Dynamic prospective study conducted in two cohorts of health care workers (HCW) (healthy and infected). Each cohort will include 675 participants.

Biological, clinical, psychological and social warning signs follow-up closely monitored during one year.

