##### *Sample Size Estimation*

In a one-way ANOVA study, sample sizes of 522, and 522 are obtained from the 2 groups whose means are to be compared. The total sample of 1044 subjects achieves 90% power to detect differences among the means versus the alternative of equal means using an F test with a 0.05 significance level. The size of the variation in the means is represented by the effect size  $\eta^2 = \sigma_m^2 / (\sigma_m^2 + \sigma^2)$ , which is 0.01 [10-13]

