##### *Dropout-Inflated Sample Size*

Average Group Sample Size n	Group	Dropout Rate	Sample Size Ni	Dropout-Inflated Enrollment Sample Size Ni'	Expected Number of Dropouts Di
522	1-2	10%	522	580	58
	Total		1044	1160	116

Average Group Sample Size n	Group	Dropout Rate	Sample Size Ni	Dropout-Inflated Enrollment Sample Size Ni'	Expected Number of Dropouts Di
522,00	1 - 2	10%	522	580	58
	Total		1044	1160	116

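### Hypothesis and aim 3 treat cytokines as biomarkers of disease progression, but the planned tests between severity classes and sexes can show neither progression nor useful discrimination.

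*Combined protocol and SAP*

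**What the plan says.** Section 5.1 states as hypothesis 3: "Cytokines are good biomarkers to identify COVID-19 disease progression". Section 5.2.2 gives aim 3 as: "To analyze differentially expressed cytokines as biomarkers of disease progression in early, mid, and long periods of immunization". Outcome 10 in section 6.6.2 and the heading of section 6.8.2.3 also speak of progression.

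The text of 6.8.2.3 then says that levels will be "compared between different clinical spectrum or sexes to determine their role as a biomarker of disease type". The tests are t-test or Mann-Whitney between sexes and ANOVA or Kruskal-Wallis between clinical spectrums, chosen after a Shapiro test. The criterion is given as "Significance level will be set to 0.05". Outcome 10 repeats these tests for a 45-plex panel at seven time points from baseline to 12 months.

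Section 6.5 divides infected participants into three severity classes. It also separates a recent infected pre-cohort (less than 15 days from a positive RT-PCR) from a non-recent one (more than 15 days).

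**The concern.** A progression biomarker has to be measured before the outcome it is meant to foretell, and it has to separate people who will worsen from people who will not. Comparing group levels at a significance level does neither. It shows that average level or rank differs between classes. It does not show that the difference came first, or that it is large enough to classify an individual.

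At stake is what the study can conclude for its third hypothesis. Section 4 gives the motive as added value in prognosis and information for therapy. The planned analysis cannot supply that, and the plan does not say what result would count as a good biomarker.

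**Working it through.** **1. Is there a progression analysis elsewhere?**
- Section 6.8.2.1 has longitudinal models, but they cover IgM and IgG only.
- Section 6.6.2 mentions a prognostic role for the baseline and prospective measurements but gives no method.
- Section 6.5 gives each infected person one severity class with no date. Asymptomatic and presymptomatic infection form a single class, so moving from no symptoms to illness is not captured as an outcome.
- No section names an AUC, sensitivity, specificity or cut-off, or defines a progression event.

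**2. Time order.** In Table 2 the recent infected have T-cells and cytokines at Visit 1. The non-recent infected have no Visit 1; their later cytokine samples depend on antibodies at Visit 4, and the last visits list antibodies alone. Their class differences may therefore reflect past severity. Table 5 lists Visit 1 cytokines for infected participants without this distinction, so the two tables disagree on who has an early sample.

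**3. The plan's own sample size.** It is not specific to cytokines, but it gives a scale. The plan says "sample sizes of 522, and 522 are obtained from the 2 groups whose means are to be compared" and "The total sample of 1044 subjects achieves 90% power to detect differences among the means", with η² = 0.01 and α = 0.05.
- f² = 0.01/0.99 = 0.0101; noncentrality = 1044 × 0.0101 = 10.55; df 1 and 1042.
- Power = 0.9005, and 522 is the smallest group size reaching 90%. With 10% dropout, 522/0.9 = 580 per group and 1160 in total. All stated figures reproduce.
- The design effect is d = 2f = 0.201. Under two normal distributions with equal variance, AUC = Φ(d/√2) = Φ(0.142) = 0.557. At the midpoint cut, sensitivity = specificity = Φ(d/2) = 0.54.

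**4. What a just-significant class difference means.** Section 6.1 says "Each cohort will include 675 participants". The severe-critical share is not given, so 2% to 20% is assumed. The contrast is severe-critical versus other infected:

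d = t × √(1/n₁ + 1/n₂), with t = 1.96 (675) or 1.97 (338); AUC = Φ(d/√2).

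| Infected with a sample | Severe (assumed) | d at p = 0.05 | AUC |
|---|---|---|---|
| 675 | 14 (2%) | 0.53 | 0.65 |
| 675 | 34 (5%) | 0.35 | 0.60 |
| 675 | 68 (10%) | 0.25 | 0.57 |
| 675 | 135 (20%) | 0.19 | 0.55 |
| 338 (assumed half) | 7 (2%) | 0.75 | 0.70 |
| 338 (assumed half) | 17 (5%) | 0.49 | 0.63 |
| 338 (assumed half) | 34 (10%) | 0.36 | 0.60 |

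For comparison, an AUC of 0.80 needs d = 1.19 under the same model.

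**5. Precision of a reported AUC.** The Hanley-McNeil variance is [A(1−A) + (n₁−1)(R₁−A²) + (n₂−1)(R₂−A²)]/(n₁n₂), with R₁ = A/(2−A) and R₂ = 2A²/(1+A). For A = 0.80, R₁ = 0.667 and R₂ = 0.711. With 14, 34 or 68 severe of 675, the 95% half-width is 0.14, 0.09 or 0.065. That is usable for describing severity class. An analysis restricted to later progressors would have fewer events and wider intervals.

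**The case against.** The strongest reply is that this is mainly a mismatch of words. The operative text of 6.8.2.3 already speaks of disease type, section 4 calls cytokine testing more exploratory, and this is a secondary aim of an observational cohort. That stands in part: the narrower claim is already in the analysis section, so aligning hypothesis and aim 3 with it is a natural repair. It does not remove the point, because the hypothesis, aim, outcome and heading all still promise progression.

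Four stronger readings are tempting, and the documents do not support them.
- A reader might infer that the plan treats p < 0.05 as proof of a good biomarker. It sets a significance level but never says this; it simply gives no criterion for good.
- A reader might infer that only mean differences between severity classes are tested. Rank tests and sex comparisons are also planned. Mann-Whitney can be rescaled to an AUC, but it is planned for sex, not severity, and no AUC is to be reported.
- A reader might infer that most cytokine samples come after severity is known. That fits the non-recent infected, but the split between recent and non-recent is not given.
- A reader might infer that any just-significant marker is close to useless. The AUC at the threshold depends on the unknown severe share and number sampled, and reaches about 0.70 in the sparsest case above.

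It is also fair that the severe-versus-rest contrast simplifies the plan's three-class test.

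**Conclusion.** The concern holds in this form: as written, the plan cannot answer hypothesis 3 or aim 3. It has no time-ordered analysis and no discrimination measure, and for non-recent infected participants class differences may reflect past severity. Statistical significance is compatible with weak separation: an AUC of about 0.55 to 0.65 at the threshold with 675 infected, and up to about 0.70 with half that number and 2% severe.

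These figures rest on an equal-variance normal model, a severe-critical versus rest contrast, and assumed severe and early-sample shares. The conclusion about progression rests on the text alone and needs none of them. Nothing here shows that cytokines are poor markers, or that the stated sample size is wrong for its own purpose. The change is worth making before the cytokine analysis, in proportion to a secondary aim.

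**What to change.** 1. In 6.8.2.3, for each cytokine and period, report the AUC with 95% CI for severe-critical versus other infected participants alongside the planned tests. State conclusions for hypothesis and aim 3 as association with severity class, in line with the disease-type wording already there, and not as progression.
2. Draw a progression conclusion only from recent infected participants who have a Visit 1 cytokine sample and were not yet severe-critical at that visit. Relate that level to the worst class reached later, report an AUC with 95% CI, and label it exploratory. Class at Visit 1 would have to be derived from recorded symptom dates and hospital admissions (section 6.6, items 7 and 12).
3. Reconcile Table 2 and Table 5 on who has Visit 1 cytokines.

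Item 1 costs wording and a short calculation on data already planned. Item 2 costs derivation work and may give wide intervals or too few progressors, in which case only item 1 applies.

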In fact, a major current question is if individuals who have been infected with SARS-CoV-2, whether symptomatic or asymptomatic, knowingly or unknowingly, develop permanent immunity to the virus. Answering this question is crucial for epidemiologists, policy makers, health service professionals and society at large. To do so, three different types of diagnostic tools can be used: 1) RNA-based tests to determine whether viral genes are present in nasal and throat swabs, indicating active infection (by RT-PCR); 2) Detection of antibodies against SARS-CoV-2 in plasma or capillary blood. Antibodies can also indicate active infection but, more importantly, they indicate if the individual has already been infected and is able to develop a satisfactory immune response based on the presence of these antibodies. 3) Cytokine storm testing is a more exploratory diagnostic tool that can include assessment of the presence of proinflammatory cytokines in response to SARS-CoV-2 infection. The presence of a 'cytokine storm' has been linked to disease severity and progression and to a particular feature of the pathogenic features of SARS-CoV-2 infection [4].

Different studies have shown that levels of antibody response differ depending on the clinical spectrum of SARS-CoV-1 [5]. Nevertheless, little is known regarding immune response to SARS-CoV-2. It has been observed that the highest antibody responses are presented by people with a more severe clinical spectrum, hospital admissions and intensive care units. The highest response has been shown by IgM and IgG against SARS-CoV-2 antigens [6,7]. Despite this, there are still few studies that have been able to accurately analyze the results of the immune response over a period of 12 months. However, the immune response to SARS-CoV-2 infection is heterogeneous, with clinical spectra ranging from individuals with asymptomatic infections to individuals with very severe clinical manifestations that can even lead to death. It is possible that some individuals will never develop sterilizing immunity following infection with SARS-CoV-2 or that multiple exposures will be needed for affinity maturation and development of long-lasting protection. All these points have to be explored and they are extremely important for re-vaccination criteria.

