## 6.6 VARIABLES MAIN COVARIABLES

- 1) Biological sex measured as a dichotomous variable in two categories (Male, Female)
- 2) Age (years): registered and analyzed as a continuous variable
- 3) Academic level: measured as a 5 levels variable (lower primary, completed primary, secondary, Post-secondary non-tertiary education, Short-cycle tertiary education, university).
- 4) Housing characteristics (meters, number of bedrooms, number of people in the same house, relationship, age of them)
- 5) Work variables (professional category, schedule, workplace's characteristics)
- 6) Clinical Spectrum of COVID-19 defined on procedure for action against cases of infection with the new SARS-CoV-2 coronavirus, defined according to national and international guidelines ( asymptomatic, Mild-Moderate Illness, severe-critical ) as defined in section 6.5
- 7) Clinical monitoring of COVID-19 symptoms, days of duration and monitoring Long Covid symptoms. (Table 3 , Table 4)
- 8) The date of symptom onset shall be considered as the date of appearance of the first symptoms. These symptoms, which are described in Table 2, are the confirmation of a positive RT-PCR test or antigen test (IgM (N) or IgG (N)).
- 9) Diagnostics. In the electronic medical records (EMR) for Primary Care and Hospitals, the diseases are codified using the International Classification of Diseases, version 10 (ICD-10), including the specific codes for COVID-19
- 10) Use of personal protective equipment (working and in the free time)
- 11) Medication prescribed. Classification number of drugs according to the Anatomical Therapeutic Chemical (ATC) Classification System.
- 12) Hospital admissions: admissions and emergency procedures according to the codes ICD-10 used in CMBD-HA.
- 13) Comorbidities: diabetes, hypertension, ischaemic heart diseases, other chronic comorbidities
- 14) Mortality by all causes. The initial data for the calculation of risk of death will be determined from March 15, 2020.
- 15) Psychosocial and healthy habits changes during pandemic (dream, eating, sexuality, physical activity and familiar relationship)
- 16) Laboratory Assays

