### C) Additional Immune response laboratory assays:

C1) Additionally, blood samples of HCW (infected and healthy participants) will be collected and stored for more exhaustive determinations of the immune response in later studies.

C2) INF $\gamma$  Elispot assays. To monitor both SARS-CoV-2 specific CD4+ and CD8+ T-cell responses we performed an INF $\gamma$  ELISPOT assay. The design compromises a comprehensive screening using peptide pools for the nucleocapsid, membrane, S1 and S2 regions of the spike protein described in Olvera et al., (2020) vaccines and total recombinant proteins for the nucleocapside and the spike. In brief, cells will be thawed and incubated overnight at 37°C in the presence of SARS-CoV2 peptide pools described (5ug/ml for each peptide) and PHA (15  $\mu$ g/ml), as positive control. Finally, plates were revealed with biotinylated anti-human INF $\gamma$ , streptavidin-alkaline phosphatase and its coloured substrate (Mabtech, Sweden).

IFNy secreting cells were quantified under Immuno Capture and Immuno Spot software to calculate the number of Spot Forming Cells (SFC). Cryopreserved PBMCs will be stimulated overnight with CoV-2 peptide pools (5ug/ml for each peptide) and PHA (15 µg/ml), as the positive control. Spot Forming Cells (SFC) will be counted using an INFg-ELISpot kit (Mabtech), AP-conjugate kit (BioRad) and an automated ELISPOT Reader Unit (CTL) as previously described (Dalmau et al AIDS 2014). Wells will be considered positive if they contained at least 50 spot-forming cells per 10^6 PBMCs above the background level (2X mean + 3Xstandard deviation).

C3) Citokines multiplex assay. Cryopreserved plasma samples will be used in a 45-plex assay of soluble mediators. The plates will be read with a Luminex instrument (Luminex 200, Austin Luminex, USA) and data will be analysed using MILLIPLEX Analyst 5.1 software (Merck Millipore Darmstadt, Germany). Measures will be performed in duplicates.

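### The 45-analyte cytokine panel is tested at 0.05 per test with no multiplicity procedure, and no named immune-response analysis includes age although hypothesis 2 names it

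*Combined protocol and SAP*

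**What the plan says.** **Cytokines.** Section 6.6 (laboratory assays, C3) sets the panel: "Cryopreserved plasma samples will be used in a 45-plex assay of soluble mediators". Secondary outcome 10 in Section 6.6.2 repeats this and gives the time frame as "Baseline, 7 days, 15 days, 3, 6, 9 and 12 months after the beginning of the study". Section 6.8.2.3 compares levels between clinical spectrums and between sexes "to determine their role as a biomarker of disease type". It uses "t-test or Mann-Whitney to compare between sexes and ANOVA or Kruskal-Wallis to compare between clinical spectrums", chosen after a Shapiro check, and adds: "Significance level will be set to 0.05". The analysis serves hypothesis 3 (cytokines as markers of progression) and the third secondary aim.

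**Post-hoc tests.** Section 6.8.2.2 foresees post-hoc analyses across the clinical spectrum but names neither a method nor an adjustment.

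**Age.** Hypothesis 2 in Section 5.1 reads: "The immune response is conditioned by age, sex and other clinical variables". Section 6.6 lists age as a main covariable, "registered and analyzed as a continuous variable". The introduction to Section 6.6.2 says that prognostic roles and confounding will be assessed.

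**The concern.** There are two separate gaps.

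First, under the stated rule every analyte with no true difference has a 5% chance of being flagged, for each factor tested. Nothing in the plan limits how many of the flagged cytokines are false. A reader of the resulting biomarker list could not tell how much of it to believe.

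Second, a stated hypothesis says that age conditions the immune response, but no method is given that could test this. The named group comparisons take one factor at a time. A cytokine or antibody difference between severity groups therefore could not be separated from any age or sex difference between those groups, although Section 6.6.2 says confounding is to be examined.

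**Working it through.** **The plan's own figure.** The documents state no error rate for the cytokine panel. The only computed figure is the sample size in Section 6.4: two groups, η² = 0.01, level 0.05, power 90%. With f² = 0.01/0.99 = 0.0101 and a noncentral F on 1 and N − 2 degrees of freedom, 522 per group gives power 90.05%. The figure reproduces. It is for a single F test at 0.05 and does not cover a panel of 45.

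**Inputs for the panel.** The 45 analytes come from Section 6.6 (C3) and outcome 10. The level of 0.05 and the two factors come from Section 6.8.2.3. The number of truly null analytes, m, and the correlation ρ between test statistics are not in the documents. They are assumed below and shown as ranges.

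**Expected false positives, one factor at one time:** m × 0.05. This does not depend on correlation.

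**Chance of at least one false positive:** 1 − 0.95^m if independent. For equicorrelated normal statistics it is 1 − E[{Φ((1.96 − √ρ·g)/√(1−ρ)) − Φ((−1.96 − √ρ·g)/√(1−ρ))}^m], where g is standard normal.

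| Null analytes m | Expected false positives | Independent | ρ = 0.3 | ρ = 0.5 |
|---|---|---|---|---|
| 45 | 2.25 | 0.901 | 0.778 | 0.598 |
| 35 (assumed) | 1.75 | 0.834 | 0.707 | 0.541 |
| 22 (assumed) | 1.10 | 0.676 | 0.569 | 0.439 |

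At m = 45 and ρ = 0.9 the chance is still about 0.19.

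**Share of flagged analytes that are false** (ratio of expected counts; null counts and power all assumed):
- 22 null, 23 real, power 80%: 1.1/(1.1 + 18.4) = 0.056
- 35 null, 10 real, power 50%: 1.75/(1.75 + 5) = 0.259
- 35 null, 10 real, power 30%: 1.75/(1.75 + 3) = 0.368

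**Age, analysis by analysis:**

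| Place | Method | Factors |
|---|---|---|
| 6.8.2.1, LOESS | smoothed curves | clinical condition or gender |
| 6.8.2.1, NLME | nonlinear mixed model | spectrum, sex |
| 6.6.2 outcome 9; 6.8.2.2 | ANOVA/Kruskal-Wallis; t/Mann-Whitney | spectrum; sex |
| 6.6.2 outcome 10; 6.8.2.3 | the same tests | spectrum; sex |

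None includes age, and the group tests as specified cannot take a continuous predictor. The nearest text, in Section 6.8.2.2, relates the incidence of infection, not the immune response, to sociodemographic data. Section 6.8.1 compares the cohorts with each other. The Abstract mentions age in relation to immune response only under Future plans, as a possibility.

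**The case against.** **The work is exploratory.** This is the strongest reply. Sections 6.8.1 and 6.8.2.2 call their bivariate analyses exploratory, and the Background calls cytokine testing a more exploratory tool. The study is an observational cohort whose primary aim is to build the cohort. An unadjusted screen can be defended if it is labelled as one. This softens the point but does not remove it. Section 6.8.2.3 does not use the label, sets a significance level, and serves a stated hypothesis and a listed secondary outcome. A label would also leave the number of false flags unbounded.

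**The all-null case is unrealistic.** For severity that is fair. The Background says the presence of a cytokine storm "has been linked to disease severity and progression". A reader might infer a 90% chance that the study reports a false cytokine, or that most flagged cytokines will be false. The documents support neither, since both depend on how many analytes are null, on their correlation and on power. The partial-null rows are there for that reason.

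**Counts across all visits.** It is tempting to multiply by the seven listed time points. Table 5, however, shows no cytokines at visits 2 and 3, and no section says that tests are repeated at each visit. No total across visits can be supported.

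**Age is not ignored.** A reader might infer that the plan leaves age out. It does not: Section 6.6 states an intention to analyse it, and Future plans mention it. What is missing is a named method.

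**Adjustment answers a different question.** Whether a cytokine marks disease type can legitimately be asked without adjustment. This stands, so the age-adjusted analysis should supplement the unadjusted comparison and not replace it.

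**Conclusion.** Both gaps hold. It is certain from the text that Section 6.8.2.3 has no multiplicity procedure and that no named immune-response analysis includes age.

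The size of the first gap is conditional. For one factor at one time it is 2.25 expected false positives if all 45 analytes are null, and proportionately fewer otherwise. The probability of at least one depends on the assumed correlation.

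The age gap is a missing method for part of hypothesis 2. The documents give no figure from which any age confounding could be sized, and they do not show that the severity groups differ in age.

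The changes should be made. They do not rank higher because cytokines and the other immune-response measures are secondary outcomes.

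**What to change.** 1. **Section 6.8.2.3:** apply Benjamini-Hochberg at a 5% false discovery rate across the 45 analytes, separately for spectrum and for sex. State which periods or visits are tested, and include any period-specific tests in the family.
2. **Section 6.8.2.2:** name the post-hoc method and adjust its pairwise p-values across the three spectrum categories.
3. **Age:** beside the unadjusted comparisons, fit a regression of each immune-response outcome, on a suitable scale, on spectrum, age (continuous) and sex. Report the age coefficient as the test of the age part of hypothesis 2. Age terms in the NLME are optional.

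**Cost.** The change needs SAP wording and some extra modelling. Age, sex and spectrum are already collected (Section 6.6), so no new data are needed. Fewer cytokines will be called significant, and some real differences may be missed. For scale, take the plan's own effect size with 522 per group. Bonferroni over 45 tests (0.05/45 = 0.0011) would cut two-group power from 90% to 49%. Benjamini-Hochberg over the same 45 tests rejects everything Bonferroni rejects and nothing above 0.05, so its power lies between those values. The sample size was not built for the cytokine comparisons, so these figures are only a guide.
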